23.02.2021

**COMPARISON OF GLIDESCOPE® TITANIUM
(VERATHON) AND FLEXIBLE INTUBATION VIDEO
ENDOSCOPE® (FIVE, STORZ) IN TERMS OF
INTUBATION SUCCESS IN INFANTS WITH PIERRE
ROBIN SEQUENCE**

[name]

[name]

[name]

MATERIAL – METHOD

Our study is a prospective randomized controlled trial. Intubation success and intubation times were compared with Flexible Intubation Video Endoscope (FIVE)® or GlideScope® Titanium devices in patients with Pierre Robin Sequence. Hacettepe University Clinical Research Ethics Committee (Date: 23.02.2021, Decision No: 2021/4-16 KA-20115) and Turkish Medicines and Medical Devices Agency (TITCK) approval letter was obtained (Number; E-688699933-511.06- 365554).

Patients with Pierre Robin Sequence who were younger than 12 months and underwent elective surgery under general anesthesia between March 2021 and December 2023 were included in the study. Patients requiring emergency surgery, patients requiring rapid sequence intubation, patients who had already been intubated or tracheostomized to the operating room, patients who would not be operated on under general anesthesia, patients who did not have family consent and who could not provide informed consent were excluded from the study. Randomization was performed by a research assistant using a computer to generate random numbers 1 and 2 and was terminated when the minimum number of patients in each group was reached. Number 1 was assigned to the GlideScope® Titanium and number 2 was assigned to the Flexible Intubation Video Endoscope® (FIVE). Both devices are routinely used successfully as the first choice in this patient group in our clinic. Randomization was concealed in a sealed envelope from the operator and the operator was informed after parental consent to participate in the study was obtained. Endotracheal intubation was performed by 2 faculty members who were experts in the field. Since faculty members would not know the assigned intubation device before the patient was taken to the operating room, both devices were kept ready in the room. In randomized patients, GlideScope® Titanium (Verathon) or Flexible Intubation Video Endoscope® (FIVE) 11301 abx, 2.85 mm (Storz) devices were compared in terms of intubation success as the primary outcome and our specified secondary outcome measures.

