and selection of the endotracheal tube to be used were not changed for the purpose of the study. The operator used the selection he/she made routinely for the patient according to his/her body weight and physical development. The number of attempts for successful intubation and the duration were recorded by an unblinded research assistant. The chronometer was started when the FFB or the videolaryngoscope started to pass through the patient's mouth/nose and the chronometer was stopped when the ventilation of the lungs was confirmed with the end tidal carbon dioxide trace and this time was recorded as the successful intubation time. The time between the FFB or the videolaryngoscope passing through the mouth/nose and the best glottic view was obtained was recorded as the best glottic visualization time. The operator reported the percentage of glottic opening score (POGO) and Cormack Lehane scores after obtaining the best glottic visualization in the Glidescope group. In accordance with standard clinical practice, the operator was allowed to perform optimal external laryngeal manipulation as required during laryngoscopy. Endotracheal tube passage time was defined as the intubation time minus the best glottic visualization time and was recorded. Failed intubation was defined as an intubation attempt exceeding 120 seconds or removal and repositioning of the airway device from the mouth/nose or esophageal intubation. If the intubation attempt exceeded 120 seconds or the patient's SpO₂ value fell below 85% and/or bradycardia occurred at any stage of the procedure, the attempt was planned to be terminated if it was ongoing and mask ventilation of the patient was provided. Airway management after unsuccessful intubation was managed in accordance with the difficult airway algorithm under the responsibility of the faculty member in charge. Complications during the attempt were recorded. Complications were determined as esophageal intubation, desaturation defined as SpO₂<90%, airway bleeding, soft tissue damage, bradycardia (heart rate below 90 beats/min), systolic hypotension (below 60 mmHg for 0-1 month, 70 mmHg for 1-12 months), dysrhythmia, and cardiac arrest. During this entire process, a difficult airway cart and sugammadex were kept ready to be applied in case of emergency. In patients who were evaluated to have complications or who might need a tracheostomy, a pediatric ENT specialist and a surgical tracheotomy set were present in the operating room. All these preparation processes and procedures are routinely applied in this manner in our clinic.

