IBM SPSS Statistics ver. 25 (IBM Corporation, Armonk, NY, USA) program was used for data analysis. Whether the distribution of quantitative variables was distributed close to normal was examined with the Shapiro-Wilk test, and whether the assumption of homogeneity of variances was met was examined with the Levene test. Descriptive statistics were expressed as median (25th percentile-75th percentile) for quantitative variables, while qualitative variables were shown as number of cases and (%). As a result of the goodness-of-fit tests, the significance of the differences between the groups in terms of variables for which the parametric test statistics assumptions were not met was examined with the Mann Whitney U test. In the analysis of categorical data, if the expected frequency was below 5 in at least 1/4 of the cells in 2x2 cross tables, the categorical data in question were evaluated with Fisher's exact probability test, and when the expected frequency was between 5-25, the Continuity Corrected χ^2 test was used. RxC (in case at least one of the categorical variables in the row or column has more than two results) in the cross tables, if the expected frequency is below 5 in at least 1/4 of the cells, the categorical data in question were evaluated with the Fisher Freeman Halton test. The results were considered statistically significant for $p<0.05$.

Power Analysis

It is not known exactly how much the difference in intubation time is significant in the clinic. There are very few studies in the literature on this subject in pediatric patients and in the patient group with PRS.

In a study conducted by Fiadjoe et al. on a pediatric PRS mannequin, GlideScope Cobalt videolaryngoscope and FFB were compared in terms of their success in the first intubation attempt and no difference was found (88.3% vs. 85%, respectively, $p=0.59$). Although there was a statistically significant difference in intubation time between the two groups, this difference was not considered clinically significant (median 30.9 s for FFB and 25.1 s for GCV, $p=0.04$). It was interpreted that significant adverse cardiopulmonary events such as arterial oxygen desaturation, bradycardia and hypotension were unlikely to occur during this period.

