Again, Fiadjoe et al. In a study conducted by in a pediatric patient group, Glidescope videolaryngoscope and conventional direct laryngoscope were compared in terms of intubation success and intubation time. In this study, the significant endotracheal intubation time difference was accepted as 10 seconds. In our study, based on the existing literature studies and our clinical experience, the significant endotracheal intubation time difference was accepted as

10 seconds, and the total sample size was calculated as 46 patients, with 23 patients in each group for $\alpha=0.05$ and 90% power. Patient recruitment continued until the minimum number of patients in each group was reached.

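### The 2x2 testing rule is valid but conservative for the primary outcome at 23 per arm; Boschloo's exact test would keep the 5% level and gain modest power when one device does clearly worse

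*Combined protocol and SAP*

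**What the plan says.** The Material – Method section says the devices "were compared in terms of intubation success as the primary outcome". Failure is a yes/no event: "Failed intubation was defined as an intubation attempt exceeding 120 seconds", or taking the device out and repositioning it, or placing the tube in the esophagus.

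The Statistical Analysis section names no test specifically for this outcome, so its general rule for 2x2 tables applies. Fisher's exact test is used "if the expected frequency was below 5 in at least 1/4 of the cells in 2x2 cross tables", and "when the expected frequency was between 5-25, the Continuity Corrected χ^2 test was used". Results are significant at p below 0.05. Categorical results are described by counts and percentages; no effect estimate or confidence interval is planned.

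The Power Analysis section sets 23 infants per group from a 10-second difference in intubation time, which is a secondary outcome. The only success rates in the document are 88.3% and 85%, first-attempt rates from a manikin study.

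**The concern.** Fisher's test is known to run below its nominal level in small samples, and the continuity correction is designed to imitate Fisher. With 46 infants, no expected count can exceed 23, so every 2x2 table of success goes to one of these two tests. If both leave much of the 5% unused, some real differences in success will be reported as non-significant even though a test with the same error guarantee would have detected them. This matters more here because the primary outcome has no power calculation of its own.

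**Working it through.** **Inputs from the document.** Binary primary outcome, 23 per arm, the two-branch rule, p<0.05, and the manikin rates of 88.3% and 85%.

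**Assumptions.** Two-sided testing, one success/failure result per infant, and exactly 23 per arm. All comparator rates other than 85% are assumed.

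**The plan's own figure.** The document gives no size or power for the success comparison. The 23 per group cannot be reproduced because no standard deviation for intubation time is stated. With n = 2(1.960 + 1.282)²SD²/10², 23 results if the SD is about 10.24 to 10.46 s. I take 23 as given.

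**Method.** List all 24 × 24 = 576 possible results (x₁, x₂). Apply the plan's rule to each: Fisher if the smallest expected count, min(x₁+x₂, 46−x₁−x₂)/2, is below 5; otherwise the continuity-corrected chi-square. For Boschloo's test, order the tables by the two-sided Fisher p-value and take the largest tail probability over a fine grid of common success rates. Size and power are then sums, over the rejected tables, of Bin(x₁; 23, p₁) × Bin(x₂; 23, p₂), with p₁ = p₂ for size.

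**Rejection regions.** The plan's rule rejects 300 tables, exactly those that Fisher alone rejects, so the chi-square branch adds nothing. Boschloo rejects those 300 plus 20 more.

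**Size at a common success rate.**

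| Rate | Plan | Boschloo |
|---|---|---|
| 50% | 0.0260 | 0.0473 |
| 80% | 0.0251 | 0.0343 |
| 85% | 0.0232 | 0.0274 |
| 88.3% | 0.0192 | 0.0205 |
| 95% | 0.0031 | 0.0031 |
| Maximum over all rates | 0.0260 | 0.0475 |

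With unequal arms of 23 vs 25 to 30, the plan's size is 2.3% to 3.1% for rates from 50% to 86.65%.

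**Power.**

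| True rates | Plan | Boschloo |
|---|---|---|
| 88.3% vs 85% | 0.028 | 0.032 |
| 88.3% vs 70% | 0.24 | 0.28 |
| 88.3% vs 60% | 0.50 | 0.57 |
| 85% vs 50% | 0.64 | 0.72 |
| 95% vs 70% | 0.533 | 0.567 |
| 99% vs 75% | 0.635 | 0.637 |

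**Where the verdicts differ.** The 20 extra tables are 10 pairs, each counted in both directions. All have at least 10 failures and at least 10 successes among 46.

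**Example on that boundary: 21/23 vs 15/23.** There are 10 failures, so the smallest expected count is 10 × 23/46 = 5. That is not below 5, so the continuity-corrected branch applies:

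χ² = 46(|21×8 − 2×15| − 23)² / (23×23×36×10) = 46 × 115² / 190,440 = 3.19, p = 0.074.

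Boschloo gives p = 0.038. A second example, 19/23 vs 12/23, gives 0.059 under the plan and 0.030 under Boschloo.

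**The case against.** The strongest reply is that nothing here is wrong. Fisher and the corrected chi-square are standard, the rule is stated, and the error rate stays below 5%. Whether to condition on the table margins is a methodological choice. That the rule is valid stands in full. The conditioning argument carries less weight, because the plan states no conditional principle; it gives an expected-count convention for categorical data in general. Boschloo's test gives up no type I error protection at the 5% level.

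The second reply is that the gain is absent where the document's own figures lie, and this also stands. At 88.3% vs 85%, about 23 × (0.117 + 0.150) = 6.1 failures are expected, short of the 10 needed for any verdict to change. The protocol describes both devices as established first-line tools in this clinic, and nothing in it points to a success rate near 50% or 60%.

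A reader might therefore infer from the 2.6% figure that a better test recovers the whole unused half of the 5%. It does not: 4.75% is Boschloo's maximum, reached near a 50% common rate, and at a common 88.3% its own size is only 2.05%.

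A reader might also want to extend the change to every complication table. The calculations do not support that, because rare events gain almost nothing: power at 5% vs 15% is 9.7% against 9.9%, and at 2% vs 10% it is 4.8% under both.

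**Conclusion.** The point holds as a modest efficiency gain. With 23 per arm and two-sided testing, the plan's rule has a true size of at most 2.6%. Boschloo's test keeps the size at or below 5% and is never less powerful. It adds roughly 3 to 8 percentage points at most differences that a trial of this size could plausibly detect, and close to nothing when success is high in both arms.

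Two stronger readings should be resisted. One is that the stated 5% level is breached; the departure is on the conservative side. The other is that changing the test makes the trial adequately powered for its primary outcome. At 88.3% vs 85%, 90% power would need about 2,231 per arm, and sizing the trial on intubation time is the larger weakness.

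The result rests on one binary outcome per infant. If success were analysed as number of attempts with more than two levels, the plan's separate rule for larger tables would apply instead.

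**What to change.** In the Statistical Analysis section, add one sentence for the primary outcome only: intubation success will be compared by Boschloo's exact unconditional test at two-sided 0.05, with the risk difference and a score-type 95% confidence interval (Miettinen-Nurminen or Newcombe). The uncorrected chi-square and Fisher mid-p are not substitutes, since each reaches a maximum size of 5.4% here.

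If outcomes have already been seen, keep the existing rule as the main test and present Boschloo's as a labelled sensitivity analysis. The interval is worth reporting either way, because it shows which differences remain plausible after a non-significant result.

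The cost is one sentence and possibly software other than SPSS 25. No extra patients or data are needed.
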